#### 2.4.1 Baseline studies

Performed within 7 days before starting treatment. If Clinical evaluation laboratory work was also performed within 7 days before starting treatment, then those values can be used for baseline evaluation.

- Hematology (Complete blood count plus differential and platelet count)
- Acute care panel (Na+, K+, Cl, CO2, glucose, BUN, creatinine)
- LDH
- Pre-albumin
- Pancreatic enzymes (amylase, lipase)
- Hepatic panel (alkaline phosphatase, ALT, AST, total bilirubin)
- Mineral panel (albumin, calcium, magnesium, phosphorus)
- Thyroid function tests

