### **3.2.1 Durvalumab**

#### **3.2.1.1 Durvalumab doses and treatment regimens**

The initial dose of durvalumab (Cohort 1) is 1500 mg IV every 4 weeks for up to 52 weeks. Please note, at the end of each maintenance cycle there is a 2 week window in order to allow the patients sufficient time to recover from biopsies prior to continuing treatment. Refer to the schema for a detailed description of Durvalumab administration weeks.

Study treatment should be discontinued prior to 12 months if there is confirmed PD, initiation of alternative cancer therapy, unacceptable toxicity, withdrawal of consent, or if other reasons to discontinue study treatment occur.

Subjects who have a dose interruption due to toxicity at any point in the first 12 months of treatment may resume treatment and complete the 12-month treatment period. For patients without recurrent high grade disease and who are tolerating therapy well, optional maintenance therapy may be continued in the second year. The maintenance dose will be durvalumab 1500 mg administered intravenously once every 3 months to provide an immune boost. During that second year, as per standard of care for high grade disease, cystoscopy and urine cytology will be performed every 3 months. This is depicted graphically in the schema in the optional maintenance section.

No incompatibilities between durvalumab and polyvinylchloride or polyolefin IV bags have been observed. Dose of 1500mg durvalumab (for patients >30 kg in weight) will be administered using an IV bag containing 0.9% (w/v) saline or 5% (w/v) dextrose, with a final durvalumab (MEDI4736) concentration ranging from 1 to 20 mg/mL, and delivered through an IV administration set with a 0.2- or 0.22- $\mu$ m in-line filter.

Add 30.0 mL of durvalumab (MEDI4736) (ie. 1500 mg of durvalumab (MEDI4736)) to the IV bag. The IV bag size should be selected such that the final concentration is within 1 to 20 mg/mL. Mix the bag by gently inverting to ensure homogeneity of the dose in the bag.

For patients who lose weight (<30 kg) during the course of the trial and maintain their enrollment ECOG status, further treatment with durvalumab will be weight based. The dose volume of durvalumab and number of vials needed for the subject to achieve the accurate dose will be calculated according to [Appendix B](#).

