Urine cytology		X						X (every 3 months preceding each cystoscopy as per SCHEMA )	
EpCAM determination		X						Last biopsy on trial	
Tissue PD-L1 assay		X						Last biopsy on trial	
Hepatitis B and C; HIV	X								
Urine hCG or serum $\beta$ hCG 	X 			Week 4		Week 8	X	Prior to each durvalumab dose	

*Abbreviated Title: Durvalumab & Vicineum for NMIBC*

*Version Date: 05/22/2025*

SCHEDULE OF STUDY ASSESSMENTS: Screening (Weeks -12 to -1), Induction Phase (Weeks 1 – 12), and Post-Induction Evaluation (All assessments can be performed within +/- 7 days of scheduled assessment to accommodate holidays and scheduling difficulties)								
Assessments to be performed at the times stipulated in the table and as clinically required in the management of the subject  .	Screening	Baseline	All assessments to be performed pre-infusion unless stated otherwise					
			Week 1	Weeks 2 - 5	Week 6	Weeks 7 - 11	Week 12	Post-Induction and Maintenance
Day	-84 to -1	-7 to 0						
Week	-12 to -1	-1						
Durvalumab administration 				Starting Week 2		Week 6 Week 10		Every 4 weeks resuming in week 15 and as per SCHEMA . Every 3 months if optional maintenance performed after first 12 months.
Vicineum administration 			X	X	X	X	X	Every 2 weeks resuming in week 15 and as per SCHEMA .

SCHEDULE OF STUDY ASSESSMENTS: Screening (Weeks -12 to -1), Induction Phase (Weeks 1 – 12), and Post-Induction Evaluation (All assessments can be performed within +/- 7 days of scheduled assessment to accommodate holidays and scheduling difficulties)									
Assessments to be performed at the times stipulated in the table and as clinically required in the management of the subject  .	Screening	Baseline	All assessments to be performed pre-infusion unless stated otherwise						Post-Induction and Maintenance
			Week 1	Weeks 2 - 5	Week 6	Weeks 7 - 11	Week 12		
Day	-84 to -1	-7 to 0							
Week	-12 to -1	-1							
Physical examination including weight 	X	X		Week 2		Weeks 6, 10	X	Targeted physical examination as needed.	
Vital signs (pre- during and post- durvalumab infusion; pre- and post-Vicineum drainage) 	X	X	All treatment visits						
Electrocardiogram 	X			Week 2		If clinically indicated		If clinically indicated	

**Abbreviated Title:** Durvalumab & Vicineum for NMIBC

**Version Date:** 05/22/2025

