SCHEDULE OF STUDY ASSESSMENTS: Screening (Weeks -12 to -1), Induction Phase (Weeks 1 – 12), and Post-Induction Evaluation (All assessments can be performed within +/- 7 days of scheduled assessment to accommodate holidays and scheduling difficulties)									
Assessments to be performed at the times stipulated in the table and as clinically required in the management of the subject  .	Screening	Baseline	All assessments to be performed pre-infusion unless stated otherwise						Post-Induction and Maintenance
			Week 1	Weeks 2 - 5	Week 6	Weeks 7 - 11	Week 12		
Day	-84 to -1	-7 to 0							
Week	-12 to -1	-1							
Adverse event/serious adverse event assessment			All visits						
Concomitant medications		X	All visits						
ECOG performance status	X	X			X				
Acute care panel 	X	X	X	X	X	X	X	Every 2 weeks	
LDH	X	X	X	X	X	X	X	Every 2 weeks	
Pre-albumin		X							
Pancreatic enzymes (amylase, lipase)	X	X	X	X	X	X	X	Every 2 weeks	

**Abbreviated Title:** Durvalumab & Vicineum for NMIBC

**Version Date:** 05/22/2025

SCHEDULE OF STUDY ASSESSMENTS: Screening (Weeks -12 to -1), Induction Phase (Weeks 1 – 12), and Post-Induction Evaluation (All assessments can be performed within +/- 7 days of scheduled assessment to accommodate holidays and scheduling difficulties)									
Assessments to be performed at the times stipulated in the table and as clinically required in the management of the subject  .	Screening	Baseline	All assessments to be performed pre-infusion unless stated otherwise						Post-Induction and Maintenance
			Week 1	Weeks 2 - 5	Week 6	Weeks 7 - 11	Week 12		
Day	-84 to -1	-7 to 0							
Week	-12 to -1	-1							
Hepatic panel	X	X	X	X	X	X	X	Every 2 weeks	
Mineral panel	X	X	X	X	X	X	X	Every 2 weeks	
Thyroid function tests (TSH and fT3 and fT4) 	X	X		Week 2		Week 6 Week 10		Prior to each durvalumab dose	
Hematology 	X	X		Week 2 Week 4	X	Week 8	X	Prior to each durvalumab dose	
Urinalysis	X	X	X	X (weekly)	X	X (weekly)	X	X (prior to each Vicineum treatment)	
Urine culture and sensitivity		X							

SCHEDULE OF STUDY ASSESSMENTS: Screening (Weeks -12 to -1), Induction Phase (Weeks 1 – 12), and Post-Induction Evaluation (All assessments can be performed within +/- 7 days of scheduled assessment to accommodate holidays and scheduling difficulties)									

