  - If the infusion takes longer than 60 minutes then blood pressure and pulse measurements should be collected every 30 minutes ( $\pm 5$  minutes) and as described above or more frequently if clinically indicated.
7. ECG during screening required to measure QTc as specified above and 1 ECG is needed while on treatment (pre-durvalumab infusion) and as clinically indicated. ECGs should be obtained after the patient has been in a supine position for 5 minutes and should be recorded while the patient remains in that position. In case of clinically significant ECG abnormalities, including a QTcF value  $>470$  ms, 2 additional 12-lead ECGs should be obtained over a brief period (e.g., 30 minutes) to confirm prolongation. If screening laboratory assessments are performed within 3 days prior to Day 1, they do not need to be repeated at Day 1.
8. Free T3 and free T4 will only be measured if TSH is abnormal. They should also be measured if there is clinical suspicion of an adverse event related to the endocrine system. During maintenance phases 4-7, TSH will be drawn prior to each durvalumab dose and subsequently 4 weeks and 8 weeks after durvalumab administration.
9. Can be given without contrast if severe contrast allergy or renal function does not allow contrast administration per institutional recommendations. MRIs will be done per PI discretion and when clinically indicated.
10. First void after Vicineum administration in Week 1.
11. First void after the next morning after Vicineum administration in Week 1.
12. Day 8 void prior to Vicineum administration in Week 2.
13. H&P, Labs including renal, liver, complete blood count + platelets, coagulation studies monthly for up to 90 days after last immunotherapy.
14. End of treatment visit will occur 90 days after the last dose of immunotherapy. If clinically indicated, patients may continue to be followed by phone or clinic visits beyond that time and up to a year at the NIH/NCI or their local urologist.
15. Per PI discretion, a remote evaluation may be done by phone by a member of the study team. This evaluation will be conducted in compliance with NIH guidelines and FDA regulations. A patient may be asked to come to the NIH Clinical Center or may be referred to their local provider for an in-person assessment, if deemed necessary by the PI. In the case of any visits with participants' local providers, records will be obtained.

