## **3.6 CRITERIA FOR REMOVAL FROM PROTOCOL THERAPY AND OFF STUDY CRITERIA**

Prior to removal from study, effort must be made to have all subjects complete monthly safety visits (+/- 7 days) for 90 days following the last dose of study therapy. These visits will consist of H&P and labs (including renal, liver, complete blood count + platelets, coagulation studies). Patients will revert to standard of care once coming off study. If clinically indicated, patients may continue to be followed by phone or clinic visits beyond that time and up to a year at the NIH/NCI or their local urologist.

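### In optional year 2, scheduled blood counts fall to about one per 13 weeks; a count at the existing TSH draws, and one at Week 10, would close the gap cheaply

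*Combined protocol and SAP*

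**What the plan says.** All scheduling below is from the Section 3.4 Study Calendar unless stated.

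- **Durvalumab.** Infusions fall at Weeks 2, 6 and 10 in induction, then every 4 weeks from Week 15. For the second year the entry is "Every 3 months if optional maintenance performed after first 12 months". Section 3.2.1.1 agrees: "The maintenance dose will be durvalumab 1500 mg administered intravenously once every 3 months to provide an immune boost".
- **Hematology.** Counts are scheduled at screening, baseline and Weeks 2, 4, 6, 8 and 12. The post-induction and maintenance column says only "Prior to each durvalumab dose". Footnote 7, attached to this row, adds no draw.
- **Thyroid.** Tests are at Weeks 2, 6 and 10, then before each durvalumab dose. Footnote 8 adds: "During maintenance phases 4-7, TSH will be drawn prior to each durvalumab dose and subsequently 4 weeks and 8 weeks after durvalumab administration".
- **Chemistry.** The acute care, LDH, pancreatic, hepatic and mineral panels are every 2 weeks throughout maintenance.
- **After treatment.** Footnote 13 lists "complete blood count + platelets, coagulation studies monthly for up to 90 days after last immunotherapy".
- **Unscheduled tests.** The calendar header allows assessments whenever clinical management requires them. Scheduled assessments carry a window of 7 days either side.

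**The concern.** A per-dose rule works while durvalumab is given every 4 weeks. Once the dose moves to every 3 months, the same rule thins the counts to the same interval. Footnote 8 recognises this for TSH, and the chemistry panels are not tied to the infusions. Hematology is left as the only routine safety blood test at about 13-week spacing.

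The documents name the conditions that a count would reveal: immune thrombocytopenia (Section 14.1.2, Table 1), haemolytic anaemia and immune-mediated neutropenia (Section 14.1.2.1). Appendix C's table for other immune-mediated reactions asks for a hold at Grade 2 or 3 and a permanent stop at Grade 4. Those rules cannot act on a silent fall in platelets or neutrophils that nobody has measured. LDH and total bilirubin every 2 weeks give partial cover for haemolysis, but none for the other two.

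What is at stake is patient safety and, to a small degree, adverse-event capture late in treatment. A lesser matter is that the Week 10 infusion has no count of its own, although blood is drawn that week for thyroid tests.

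**Working it through.** The plan states no figure to reproduce. The check compares schedules and then bounds the yield.

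**1. Year 2 (maintenance phases 4 to 7).** The schema runs from Week 54 to Week 105: 105 − 54 + 1 = 52 weeks, or 4 cycles of 13 weeks. The infusion symbols are not readable in the text, so one infusion at the start of each cycle is inferred from the stated 3-month interval.
- Counts now: 4, at weeks 0, 13, 26 and 39 of the year. Longest gap: 13 weeks.
- TSH under footnote 8: 4 × 3 = 12 draws, spaced 4, 4 and 5 weeks.
- Chemistry panels: 52 / 2 = 26.
- Counts if drawn with each TSH sample: 12. Longest gap: 5 weeks. Added: 8 per patient.

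**2. Week 10.** Infusions {2, 6, 10} minus counts {2, 4, 6, 8, 12} leaves {10}. Gaps between induction counts are now 2, 2, 2 and 4 weeks. With Week 10 added and Week 8 kept they are 2, 2, 2, 2 and 2. Year-1 maintenance gaps remain at about 4 to 5 weeks, so the gain from 4 weeks to 2 holds within induction only.

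**3. Who could benefit.** Section 1.2.3 reports 5 responders among 12 patients at 12 weeks, half of them with a response beyond 12 months.
- Week 10: those 12 had already passed it. At most 24 − 12 = 12 patients remain, or 40 − 12 = 28 at the accrual ceiling in Section 10.2. Current accrual is not stated.
- Year 2, assuming the interim fractions hold and every such patient takes the option: 24 × 5/12 × 0.5 = 5, or 40 × 5/12 × 0.5 = 8.3. These are whole-trial figures; some of these patients may already have passed year 2.

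**4. Expected yield.** In the pooled durvalumab monotherapy data (Section 1.2.1.2), no blood-count event is among the related Grade 3 events at 0.5% or more. Taking 0.5% as an upper bound for any one such event:

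| Patients | Expected events, at most | Chance of at least one, at most |
|---|---|---|
| 24 | 24 × 0.005 = 0.12 | 1 − 0.995^24 = 11.3% |
| 8 | 8 × 0.005 = 0.04 | 1 − 0.995^8 = 3.9% |
| 5 | 5 × 0.005 = 0.025 | 1 − 0.995^5 = 2.5% |

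Immune thrombocytopenia of any grade, at 2 of 3006 (Table 1), gives 24 × 2/3006 = 0.016 and 5 × 2/3006 = 0.003. These are rates of occurrence over a whole course of monotherapy. They are not rates of events missed between counts, which the documents do not allow one to estimate.

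**The case against.** The strongest reply is that this is a preference about monitoring density. Much of it stands.

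- **Week 10 breaks no rule.** A reader might infer that it violates the plan's own per-dose requirement. It does not: that requirement sits only in the post-induction column. Induction follows its own scheme, with five counts for three infusions. The Week 8 to 12 gap is no longer than the year-1 maintenance interval, and the pregnancy-test row ("Urine hCG or serum" hCG) also skips Week 10.
- **No dosing gate needs the count.** The laboratory hold criteria in Section 3.3.2 use creatinine, creatinine clearance, transaminases and bilirubin, all measured often. Appendix C acts on a cytopenia once it is found, but does not require a count before each infusion.
- **TSH is an imperfect comparator.** Table 1 gives hypothyroidism 11.5% and hyperthyroidism 5.5%, against under 0.1% for immune thrombocytopenia. This has force, but rarity alone does not explain the schedule: pancreatitis, at 0.2%, still has enzymes measured every 2 weeks.
- **Adverse-event capture is a thin argument.** Under Section 6.1, a silent, untreated laboratory change generally counts as an adverse event only if the investigator judges it clinically significant.
- **The off-treatment comparison is limited.** A reader might infer that treated patients are watched less than those who have stopped, since Section 3.6 asks for "monthly safety visits (+/- 7 days) for 90 days following the last dose of study therapy". Per 90 days that is about 3 counts against about 1. In total, however, year 2 gives about 4 counts and follow-up about 3.

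The year-2 contrast survives these points: the other routine safety bloods are kept frequent or topped up when durvalumab is spaced out, and blood counts are not.

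**Conclusion.** The point holds as an optional, low-cost improvement, with year 2 as the main part. Scheduled counts fall to about one per 13 weeks. What is left uncovered is asymptomatic thrombocytopenia or neutropenia between counts, because symptoms would justify an unscheduled test. Week 10 is secondary and matters only for patients still to pass through induction.

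The benefit is very small and falls on a number of patients that the documents do not give. The year-2 estimates rest on 12 interim patients and on inferred infusion weeks; the 13-week spacing itself needs only the stated 3-month interval.

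A reader might also infer that the safety conclusions are compromised. The documents do not support that. Both gaps lie after the 6-week DLT period, so DLT assessment and the 3+3 decisions are unaffected, and no analysis method changes.

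**What to change.** - Extend footnote 8 to the hematology row, so that in maintenance phases 4 to 7 a blood count is drawn with each TSH sample: before each durvalumab dose and 4 and 8 weeks after it.
- For any patient still to pass through induction, add Week 10 to the hematology row at the thyroid draw already scheduled, and keep Week 8.

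The cost is one small extra tube at existing draws, with no new visit or needle: 8 tubes per year-2 patient (5 × 8 = 40, or 8 × 8 = 64, on the estimates above) and 1 per remaining induction patient. There are also more results to review. The Statement of Compliance requires IRB approval before use, so the change is best bundled with the next amendment.

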## **6 DATA COLLECTION AND EVALUATION**

### **6.1 DATA COLLECTION**

The PI will be responsible for overseeing entry of data into a 21 CFR Part 11-compliant data capture system provided by the NCI CCR and ensuring data accuracy, consistency and timeliness. The principal investigator, associate investigators/research nurses and/or a contracted data manager will assist with the data management efforts. Primary and final analyzed data will have identifiers so that research data can be attributed to an individual human subject participant.

All AEs, including clinically significant abnormal findings on laboratory evaluations, regardless of severity, will be followed until return to baseline or stabilization of event. Document AEs from the first study intervention, Week 1/Day 1, through 90 days after the last administration of the study intervention. After 90 days, only adverse events which are serious and related to the study intervention need to be recorded.

An abnormal laboratory value will be considered an AE if the laboratory abnormality is characterized by any of the following:

- Results in discontinuation from the study
- Is associated with clinical signs or symptoms
- Requires treatment or any other therapeutic intervention
- Is associated with death or another serious adverse event, including hospitalization.
- Is judged by the Investigator to be of significant clinical impact
- If any abnormal laboratory result is considered clinically significant, the investigator will provide details about the action taken with respect to the test drug and about the patient's outcome.

**End of study procedures:** Data will be stored according to HHS, FDA regulations and NIH Intramural Records Retention Schedule as applicable.

**Loss or destruction of data:** Should we become aware that a major breach in our plan to protect subject confidentiality and trial data has occurred, this will be reported expeditiously per requirements in section [7.2.1](#).

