### **8.1.6 Adverse Events of Special Interest (AESI)**

An adverse event of special interest (AESI) is one of scientific and medical interest specific to understanding of the Investigational Product and may require close monitoring and rapid communication by the investigator to the sponsor. An AESI may be serious or non-serious. The rapid reporting of AESIs allows ongoing surveillance of these events in order to characterize and understand them in association with the use of this investigational product.

AESIs for durvalumab include but are not limited to events with a potential inflammatory or immune-mediated mechanism and which may require more frequent monitoring and/or interventions such as steroids, immunosuppressants and/or hormone replacement therapy. These AESIs are being closely monitored in clinical studies with durvalumab monotherapy and combination therapy. An immune-mediated adverse event (imAE) is defined as an AESI that is

associated with drug exposure and is consistent with an immune-mediated mechanism of action and where there is no clear alternate etiology. Serologic, immunologic, and histologic (biopsy) data, as appropriate, should be used to support an imAE diagnosis. Appropriate efforts should be made to rule out neoplastic, infectious, metabolic, toxin, or other etiologic causes of the imAE.

In the event of imAE or suspected imAE, the AstraZeneca study team may request relevant clinical information (including images) for those subjects who demonstrate the event, and may request the independent review by external experts based on the acquired clinical information.

AESIs observed with durvalumab include:

- Diarrhea / Colitis and intestinal perforation
- Pneumonitis / ILD
- hepatitis / transaminase increases
- Endocrinopathies (i.e. events of hypophysitis/hypopituitarism, adrenal insufficiency, hyper- and hypothyroidism and type I diabetes mellitus)
- Rash / Dermatitis
- Nephritis / Blood creatinine increases
- Pancreatitis / serum lipase and amylase increases
- Myositis / Polymyositis
- Neuropathy / neuromuscular toxicity (e.g. Guillain-Barré, and myasthenia gravis)
- Intestinal Perforations

Other inflammatory responses that are rare/less frequent with a potential immune-mediated etiology include, but are not limited to:

- Myocarditis
- Pericarditis
- Sarcoidosis
- Uveitis
- Other events involving the eye and skin
- Hematological events
- Rheumatological events
- Vasculitis
- Non-infectious meningitis

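### Patients who stop during year 1 have no scheduled thyroid test after their last durvalumab dose, and the 90-day safety visits name neither TSH nor amylase/lipase

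*Combined protocol and SAP*

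**What the plan says.** **Post-treatment visits.** Footnote 13 of the Study Calendar (3.4) specifies "H&P, Labs including renal, liver, complete blood count + platelets, coagulation studies monthly for up to 90 days after last immunotherapy". Section 3.6 says "These visits will consist of H&P and labs (including renal, liver, complete blood count + platelets, coagulation studies". Thyroid tests, amylase and lipase appear in neither.

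**Thyroid tests on treatment.** The calendar puts them at weeks 2, 6 and 10, the weeks in which durvalumab is given. Assessments are pre-infusion unless stated otherwise. After induction the entry is "Prior to each durvalumab dose". Footnote 8 adds, for the optional second year only: "During maintenance phases 4-7, TSH will be drawn prior to each durvalumab dose and subsequently 4 weeks and 8 weeks after durvalumab administration". It limits free T3 and free T4 to patients with an abnormal TSH, but also says "They should also be measured if there is clinical suspicion of an adverse event related to the endocrine system".

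**Pancreatic enzymes on treatment.** Amylase and lipase are drawn weekly through week 12 and every 2 weeks in maintenance.

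**What counts as safety data.** Section 6.1 records adverse events "through 90 days after the last administration of the study intervention". An abnormal laboratory value becomes an adverse event only if it leads to discontinuation, has signs or symptoms, needs treatment, accompanies a death or serious event, or is judged clinically important. Section 8.1.6 names hyper- and hypothyroidism and "Pancreatitis / serum lipase and amylase increases" among the events of special interest for durvalumab. Section 10.1 makes the fraction of patients with adverse events the primary endpoint, and section 10.4.2 tabulates all toxicities.

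**The concern.** The collection window and the test schedule do not match. Adverse events are collected for 90 days after treatment, with visits and blood draws about monthly, but two panels that are routine on treatment and tied to named events of special interest are not in the list. Clotting tests are in it, although on treatment they are done only when clinically indicated. The list therefore does not look like a deliberate selection of what matters most after a checkpoint inhibitor.

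At stake is uniform ascertainment. A thyroid change that follows the last durvalumab dose and causes no recognised symptom is found only if someone chooses to test. The chance of finding it then depends on when the patient stopped and on the clinician, in a trial whose primary objective is safety. The counts can only err downward, and a patient who needs treatment may be recognised late.

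**Working it through.** No sample size, power or error rate depends on this point, so there is no design figure to reproduce. The check sets the schedules side by side and then bounds the size.

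**Step 1: thyroid timing for a patient stopping in year 1**
- Induction durvalumab: weeks 2, 6, 10. Induction thyroid tests: weeks 2, 6, 10, before infusion.
- The week-10 sample reflects 2 of the 3 induction doses. Nothing scheduled reflects the third.
- Example: last durvalumab in week 10 and last Vicineum in week 12. Adverse events are then collected for 14 + 90 = 104 days after the last scheduled TSH.
- In maintenance 1 to 3 the rule is still a sample before each dose. For any stop in year 1, scheduled thyroid samples after the last durvalumab dose = 0. This does not depend on the exact maintenance dosing weeks, which cannot be read because the schema symbols are missing from the extracted text.

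**Step 2: thyroid timing in year 2**
- Footnote 8 places TSH at 4 × 7 = 28 and 8 × 7 = 56 days after each dose.
- The last scheduled TSH therefore follows the last dose, leaving 90 − 56 = 34 days untested, provided those draws are kept when a patient stops early. The text does not say whether they are.

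**Step 3: pancreatic enzymes**
- Weekly draws through week 12 mean that samples do follow the week-10 durvalumab dose while Vicineum continues.
- None is named once treatment has stopped.

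**Step 4: size**

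Rates from Table 1 in section 14.1.2 (durvalumab monotherapy, N = 3006) reproduce as printed:
- hypothyroidism 345/3006 = 11.5%
- hyperthyroidism 164/3006 = 5.5%
- pancreatitis 6/3006 = 0.2%

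The share *s* of hypothyroidism that begins after the last dose is not given anywhere, so it is an assumption, taken as 5% to 25%. Expected cases = n × 0.115 × s. The chance of at least one = 1 − (1 − 0.115 × s)^n. The values of n are 24 (planned evaluable patients) and 40 (accrual ceiling, section 10.2).

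| s | n = 24: expected | n = 24: chance of ≥ 1 | n = 40: expected | n = 40: chance of ≥ 1 |
|---|---|---|---|---|
| 5% | 0.14 | 0.13 | 0.23 | 0.21 |
| 10% | 0.28 | 0.24 | 0.46 | 0.37 |
| 25% | 0.69 | 0.50 | 1.15 | 0.69 |

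These are cases arising after the last dose. Fewer would be missed, because symptomatic patients can be tested, some laboratory changes would not meet the section 6.1 rule, and year-2 patients have the footnote 8 samples. No corresponding figure is possible for amylase or lipase rises, because the documents give no rate for them in the post-treatment period.

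**The case against.** **The events do not simply go unmeasured.** A reader might infer that they do. The documents do not support that. Monthly history and examination continue to 90 days, the calendar allows any assessment that management requires, footnote 8 calls for free T3 and T4 on suspicion of an endocrine event, and both laboratory lists open with the word *including*. This stands, and it narrows the gap to asymptomatic events. It does not close it: an open list leaves the test to discretion, and footnote 15 lets evaluations be done by phone.

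**Many isolated laboratory changes would not be adverse events.** True under section 6.1. A change that needs treatment or is judged clinically important does count, however, and it cannot be judged if it is not measured.

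**Footnote 8 need not mean what it seems to.** When dosing moves to every 3 months, TSH at 4 and 8 weeks simply keeps the four-weekly frequency of year 1. It does not prove that the authors saw a need for testing after treatment stops. This is fair: the passages leave a gap and do not contradict each other.

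**The effect on the primary endpoint is limited.** Dose-limiting toxicity is judged in the first 6 weeks and is unaffected. The adverse-event fraction counts patients, so a late thyroid event changes it only in someone with no other event. This also stands. The tabulation of toxicities and the record of events of special interest are affected more directly.

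**The pancreatic part is weaker.** Enzymes are sampled after the week-10 durvalumab dose, and pancreatitis is rare in the pooled table. It is rightly secondary, and it is not an endocrine matter.

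**Conclusion.** The point holds for patients who stop between induction and the end of maintenance 3, including those who complete year 1 and do not take the optional second year. They have no scheduled TSH after the last durvalumab dose. For all patients, neither TSH nor amylase/lipase is named in the post-treatment panel, although the 90-day collection window and the list of events of special interest cover both. The consequence is possible under-detection of asymptomatic thyroid events that need treatment or are clinically significant, and secondarily of enzyme rises.

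The size is small in absolute terms and cannot be derived from the documents. On the assumed share of 5% to 25%, about 0.14 to 0.69 hypothyroid cases would arise after the last dose in 24 patients, or 0.23 to 1.15 in 40. This also assumes that the pooled monotherapy rate applies to this combination and to patients who had few doses.

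Three stronger readings are tempting and not supported:
- That the last TSH always precedes the last dose. Footnote 8 shows otherwise for maintenance 4 to 7.
- That the pooled thyroid rate times the sample size gives the cases missed. That rate is not limited to onset after the last dose.
- That most of the trial is affected because 5 of 12 patients had responded at 12 weeks in the interim data (section 1.2.3). The text does not say that the others stopped then, and 12 patients are few to extrapolate from.

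One ambiguity remains: footnote 13 counts from the last immunotherapy without saying whether that means durvalumab or either drug.

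The change is worth making because it is specific and cheap and bears on the trial's primary objective.

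**What to change.** Reconcile footnotes 8 and 13 and section 3.6 with the 90-day window in section 6.1:
- Name TSH in the monthly post-treatment draws through 90 days, for every patient whenever treatment stops, with free T3 and T4 if TSH is abnormal, as footnote 8 already provides.
- Secondarily, name amylase and lipase in the same draws.
- State which drug's last dose starts the 90 days, and use the same wording in the calendar and sections 3.6 and 6.1.

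The cost is a few extra assays on blood already drawn at scheduled visits, plus a short amendment to the calendar and section 3.6. No visit is added and no dose or treatment rule changes. The small downside is a few more asymptomatic laboratory abnormalities to follow. For patients already past follow-up, the report should say that post-treatment thyroid and pancreatic testing was not scheduled and was done only when clinically prompted.
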